14.1 Adverse Events

An AE is any occurrence or worsening of an undesirable or unintended sign, symptom (including an abnormal laboratory finding), or disease that is temporally associated with the use of a medicinal product whether considered related to the medicinal product or not. An SAE is defined as any AE occurring at any dose that suggests a significant hazard, contraindication, side effect, or precaution. This includes but is not limited to any of the following events (21CFR§312.32):

- Death.
- A life-threatening event. A life-threatening event is any adverse therapy experience that, in the view of the investigator, places the patient or participant at immediate risk of death from the reaction as it occurred.
- Inpatient hospitalization or prolongation of existing hospitalization.
- Persistent or significant disability.
- Congenital anomaly or birth defect.

Statistical Analysis Plan

- An event that required intervention to prevent permanent impairment or damage. An important medical event that may not result in death, be life threatening, or require hospitalization may be considered an SAE when, based on appropriate medical judgment, it may jeopardize the participant and may require medical or surgical intervention to prevent one of the outcomes listed above.
- Other conditions specified in the protocol.

In addition, events that occur at a higher than expected frequency, as determined by appropriate medical judgment, may be considered SAEs.

AEs will be graded on a scale from 1 to 5 according to the following standards in the *CIT-TCAE* manual:

Grade 1 = Mild adverse event.

Grade 2 = Moderate adverse event.

Grade 3 = Severe and undesirable adverse event.

Grade 4 = Life-threatening or disabling adverse event.

Grade 5 = Death.

AEs not included in the CIT-TCAE listing, will be recorded and graded 1 to 5 according to the General Grade Definition provided as in the table below:

Statistical Analysis Plan

Table 12.1-General Severity Definition of Adverse Event

Grade	Description	Definition
Grade 1	Mild	Transient or mild discomforts (<48 hours), no or minimal medical intervention/therapy required, hospitalization not necessary (non-prescription or single-use prescription therapy may be employed to relieve symptoms, e.g., aspirin for simple headache, acetaminophen for post surgical pain).
Grade 2	Moderate	Mild to moderate limitation in activity some assistance may be needed; no or minimal intervention/therapy required, hospitalization possible.
Grade 3	Severe	Marked limitation in activity, some assistance usually required; medical intervention/therapy required hospitalization possible.
Grade 4	Life-threatening	Extreme limitation in activity, significant assistance required; significant medical/therapy intervention required hospitalization or hospice care probable.
Grade 5	Death	Death.

All AEs will be reported and graded whether they are or are not related to disease progression or treatment. The relationship of an AE to islet transplantation, which includes the transplant procedure and/or the islet product, or to the immunosuppression and/or infection prophylaxis will be defined by using the descriptors provided in Table 12.2.

Table 12.2 -Attribution of Adverse Event

Code	Description	Definition
UNRELATED CATEGORY		
1	Unrelated	This adverse event is clearly not related to allogeneic islets; the islet transplant procedure; immunosuppression or infection prophylaxis.
RELATED CATEGORIES		
2	Unlikely	The adverse event is doubtfully related to allogeneic islets; the islet transplant procedure; immunosuppression or infection prophylaxis.
3	Possible	The adverse event may be related to allogeneic islets; the islet transplant procedure; immunosuppression or infection prophylaxis.
4	Probable	The adverse event is likely related to allogeneic islets; the islet transplant procedure; immunosuppression or infection prophylaxis.
5	Definite	The adverse event is clearly related to allogeneic islets; the islet transplant procedure; immunosuppression or infection prophylaxis.

The collecting and recording procedures for AEs are described in detail in Section 8.2 of CIT-07 protocol.

14.2 Analysis of Safety Endpoints

The safety secondary endpoints in this study target AEs related to islet transplantation (transplant procedure and/or islet product) and the immunosuppression and/or infection prophylaxis.

The targeted AEs related to the islet transplantation include:

AE-IIP-1: Bleeding (>2 g/dL decrease in hemoglobin concentration)

AE-IIP-2: Segmental portal vein thrombosis

AE-IIP-3: Biliary puncture

AE-IIP-4: Wound complication (infection or subsequent hernia)

Statistical Analysis Plan

AE-IIP-5: Increased transaminase levels (>5 times ULN)

The targeted AEs related to the immunosuppression and infection prophylaxis therapy include:

AE-IP-1: Allergy

AE-IP-2: Reduction in GFR

AE-IP-3: Increase in urinary albumin excretion

AE-IP-4: Addition or intensification of anti-hypertensive therapy

AE-IP-5: Addition or intensification of anti-hyperlipidemic therapy

AE-IP-6: Oral ulcers

AE-IP-7: Lower extremity edema

AE-IP-8: Gastrointestinal toxicity

AE-IP-9: Neutropenia, Anemia, or Thrombocytopenia

AE-IP-10: Viral, Bacterial, or Fungal Infections

AE-IP-11: Benign or Malignant Neoplasms

Results will be reported for the following time points: 75 days and one year after the first and last transplant and at 2 years, and 3 years after the first and after the last islet transplant.

We will report incidence of each AEs categorized by MedDRA term and body system. Tables with relation to the islet product and to the immunosuppression will be reported. For each category, the number of resolved events will be reported. The mean, median, standard deviation and range for the number of days until the AE is resolved will also be reported. Results will be summarized using the template provided in Appendix 2.

The incidence rate of immune sensitization, defined as detection of anti-HLA antibodies at 75 ± 5 days following the first and last islet transplant and at and one year after the first and last transplant and at 2 years, and 3 years after the first and after the last islet transplants. Exact two-sided 95% confidence interval of the incidence rate will also be reported.

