In this study, five QOL measures are considered. Two scales are obtained from the SF36 questionnaire (version 2). These scales are the Summary Physical Component score (SPC) and the Summary Mental Component score (SMC). Additional QOL assessments include the Overall Health Status (OHS) measure based on the European Quality of Life (EQ-5D) instrument, the Diabetes Distress Scale (DDS), and the Hypoglycemia Fear Scale (HFS) scales.

The SF36 scales will be standardized to the US population. The EQ-5D OHS questionnaire provides two sub-scales: the Behavior subscale that is based on 10 questions and ranges from 0 to 40 and the Worry subscale that is based on 13 questions. The scale is computed as the sum of the responses to the 13 questions and ranges from 0 to 52. The DDS is based on 17 questions rated on a 6 point Likert scales and ranges from 17 to 102. The HFS has two subscales: the Behavior scale which ranges from 0 to 40 and the Worry scale that ranges from 0 to 52.

2.6 *Time to Event Outcomes*

Multiple time-to-event outcomes will also be studied. All events will be defined for the period from the first transplant to 1095 days after the last islet transplant.

- Time to death (all cause and also cardiac related) and time to cardiovascular events (death, CVA, MI)
- Time to $HbA1c \leq 6.5\%$
- Time to first severe hypoglycemia episode
- Time to $HbA1c$ decreasing by at least 1%
- Time to global treatment failure composite outcome measure defined as the time to the first occurrence of any of the following:
 - Death
 - Stroke
 - MI
 - Above the ankle amputation

All of the above will be ascertained from the SAE reports and will be adjudicated if an adjudication committee is available.

- Renal Failure (Any one of the following):
 - Initiation of dialysis; or
 - Renal transplantation
- Blindness: Visual acuity of 20/200 in both eyes.
- Poor diabetes control (if any of the following occur):
 - $HbA1c > 9\%$ and reduced less than 1% below the entry level, found 6 months or more following the first transplant and confirmed on repeat examination at least

Statistical Analysis Plan

30 days and no more than 60 days later. If confirmed, failure is the time of the initial draw;

- Three consecutive monthly HbA1c values greater than the baseline value, with the first one being 6 months or more following the first transplant; or

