2.7 Safety endpoints

Safety endpoints include the following:

At 75 ± 5 days following each transplant, at 365 ± 14 days following the first and last islet transplant(s), at 730 ± 14 days following the last islet transplant, and at 1095 ± 14 days following the last islet transplant:

- The incidence and severity of adverse events (AEs) related to the islet transplant procedure, including: bleeding (>2 g/dL decrease in hemoglobin concentration); segmental portal vein thrombosis; biliary puncture; wound complication (infection or subsequent hernia); and increased transaminase levels >5 times upper limit of normal (ULN)
- The incidence and severity of AEs related to the immunosuppression including: allergy; reduction in glomerular filtration rate (GFR); increase in urinary albumin excretion; addition or intensification of anti-hypertensive therapy; addition or intensification of anti-hyperlipidemic therapy; oral ulcers; lower extremity edema; gastrointestinal toxicity; neutropenia, anemia, or thrombocytopenia; viral, bacterial, or fungal infections; and benign or malignant neoplasms
- The incidence of change in the immunosuppression drug regimen
- The incidence of immune sensitization defined by presence of anti-HLA (histocompatibility antigen) antibodies absent prior to transplantation
- The proportion of subjects who withdraw from study treatment due to an organ transplant

At 365 ± 14 days following the first and last islet transplant and at 1095 days following the last islet transplant:

- The incidence of worsening retinopathy as assessed by change in retinal photography

3. Subgroup Analysis

A Subject may enter the study because she/he is having severe hypoglycemic events that require assistance or because she/he is unable to reduce HbA1c level to below 7.5% on Intensive Insulin

Statistical Analysis Plan

Therapy (see inclusion criterion 7 in the protocol). The latter group may be very small. However, if there are at least 6 subjects in each group, we will perform subgroup analyses that examine these two subgroups separately. Analyses will include all primary and secondary outcome measures and use the same analysis strategies that were used for those measures. Please note that power for these analyses will be very small but the results may lead to a better understanding of the mechanisms of outcome.

4. Sample Size and Power Calculations

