5.1.1 Study Period

The trial consists of three periods: (1) the pre-transplant period, which includes screening, enrollment, and wait list time; (2) the period that includes the islet transplant procedure(s); and (3) follow-up visits through 24 months following the last transplant. The study period of this trial is a 36-month follow-up after the final islet transplant. Subjects may undergo up to 3 transplants in the course of this study; the last transplant can occur not later than 8 months following the first transplant.

In the first period, individuals who meet the general inclusion criteria will be approached regarding participation in the study. After informed consent has been obtained, they will be formally enrolled into the study. Eligibility will be confirmed based on the results of the screening visit procedure detailed in Appendix 1 of the CIT-06 protocol. Enrolled subjects who meet the eligibility screening for the studies will be put on the waiting list for an islet transplant.

After completion of the screening assessments confirming eligibility for the study, a subject will undergo 12 months of intensive insulin therapy (IIT) by an experienced diabetologist (see Appendix 3). If a subject received at least 12 months of **intensive diabetes management** prior to enrollment and experienced at least one episode of **severe hypoglycemia** during that time, the subject would not be required to receive IIT while on study as long as they have a Clarke score of 4 or more. A subject is required to return to the study site for clinic visits every 3 months while undergoing IIT and while on the waitlist. Monthly HbA1c sampling between the required 3 month interval visits may be drawn locally, sent from the local lab to the study site and then shipped to the central lab for testing. Eligibility will be reconfirmed after 4 months of IIT and after 12 months of IIT. All eligibility assessments must be within the windows required for initial study enrollment. Once eligibility has been reconfirmed, a subject will be placed on the **wait list**. The subject will continue IIT while on the **wait list**.

Once a compatible islet preparation becomes available, a subject's eligibility will be re-confirmed and eligible subjects will begin immunosuppression therapy on Day -2 (Day 0 is defined as the day of transplant).

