5.2.3 Safety Population

The safety population consists of any subject in whom protocol-directed therapy (*e.g.*, induction immunosuppression) is initiated. Subjects in this population might not receive an islet transplant.

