12.3.4 Analysis for Hypoglycemia Fear Scale

Separate analyses of HFS will be computed for 75 ± 5 days after each transplant, and at one year, 2 years, and 3 years after the first and last transplants. We will calculate the sample mean and construct the 95% confidence interval of the mean DDS using the method for a continuous variable described in SAP section 9.2.2.

The longitudinal analyses will be repeated for the HFS.

12.4 *Analysis of Secondary Time to Event Outcomes*

Time to event outcomes include the following:

- Time to death (all cause and also cardiac related) and time to cardiovascular events (death, CVA, MI)
- Time to $HbA1c \leq 6.5\%$
- Time to first severe hypoglycemia episode
- Time to $HbA1c$ decreasing by at least 1%
- global treatment failure composite outcome measure defined as the time to the first occurrence of any of the following:
 - Death
 - Stroke
 - MI
 - Above the ankle amputation

All of the above will be ascertained from the SAE reports and will be adjudicated if an adjudication committee is available.

- Renal Failure (Any one of the following):
 - Initiation of dialysis; or
 - Renal transplantation
- Blindness: Visual acuity of 20/200 in both eyes.

Statistical Analysis Plan

- Poor diabetes control (if any of the following occur):
 - HbA1c > 9% and reduced less than 1% below the entry level, found 6 months or more following the first transplant and confirmed on repeat examination at least 30 days and no more than 60 days later. If confirmed, failure is the time of the initial draw;
 - Three consecutive monthly HbA1c values greater than the baseline value, with the first one being 6 months or more following the first transplant; or
 - Occurrence of two severe hypoglycemic events (requiring assistance from another person) within a three month period. Failure will occur at the time of the second hypoglycemic event.

The endpoints and the analyses in this protocol have adopted two principal time points for each transplanted subject: (1) the time of the first transplant and (2) the time of the last transplant. It is of interest to examine the time to events following each of these time points. The following analyses will be repeated using each of these milestones as time zero in the analysis. In the unlikely event that a subject has already reached an event at the time of the second transplant he/she will not be included in the analyses for that event for time from last transplant.

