For those who have been transplanted, we will compare the profiles of change over time while the subject was on waitlist to change over time after the subject has received a transplant. We begin collecting data pre-transplant when the subject becomes eligible for transplant. Time zero for the pre-transplant values will be when the subject becomes eligible for transplant. Time zero for post-transplant observations will be the day of transplant. The endpoints and times will be the same as those described in the previous section. Analysis will use the linear mixed model approach. The models will have terms for time, transplant status (pre-transplant or post-transplant), and the interaction between time and transplant status. If the interaction is significant (which we expect) then we will test for the pre-post difference at each time point. We will report means and 95% confidence intervals for the difference at each time point. We will use the method of Benjamini and Hochberg (Benjamini & Hochberg, 1995) to account for the multiplicity of tests.

14. Safety Analyses

Safety analyses will be conducted for the safety population. Summaries will be prepared for the targeted safety endpoints listed in the secondary endpoints and for all observed AEs organized by body system. The CIT consortium modified the National Cancer Institute (NCI) toxicity table to create a document relevant for trials of adult pancreatic islet transplantation. The resulting reference manual, “Terminology Criteria for Adverse Events (TCAE) In Trials of Adult Pancreatic Islet Transplantation,” provides descriptive terminology and a grading (severity) scale which will be utilized for adverse event (AE) reporting.

Regular safety analyses will be prepared for the Data Safety Monitoring Board (DSMB). These summaries will be used to monitor the overall safety profile of the study. These analyses will summarize all AE data that are available at the time of the DSMB meeting. Analyses will summarize AEs by MedDRA term and body system. Separate incidence summaries will be prepared for serious AEs, for nonserious AEs and for all AEs combined. Separate tables will summarize severity and attribution. Each AE can be attributed to the investigational agent (allogeneic islets), the immunosuppression, both or neither. Identical safety summaries will be included in the final statistical report.

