14.2.1 Statistical Analyses of Adverse Events

AEs will be analyzed according to the body system described in the *CIT-TCAE* manual. Any event that appears in a body system will be categorized into one of the five severity grades according to the *CIT-TCAE* manual or the general definition of severity given in Table 7 and analyzed accordingly. For each event, we will analyze its incidence rate per 100 person-days. Suppose for each subject, the incidence of a particular event is a Poisson process with the homogeneous incidence rate λ . At the time of analysis, if a subject is only followed r days after the initiation of induction immunosuppression, the incidence of this event is distributed according to the Poisson distribution with mean $r\lambda/100$. The maximum likelihood estimate of the

Statistical Analysis Plan

incidence rate will be obtained based on data collected from the available subjects at the analysis time. The 95% confidence interval derived using the maximum likelihood estimator theory will be also reported. The results will be summarized in the table provided in SAP Appendix 4. Moreover, we will also list all the individuals who have ever had an incident of any of the AEs listed in Appendix 5 since their initiation of induction immunosuppression.

15. Interim Analyses and Safety Monitoring Analyses

The DSMB will be convened to review safety and efficacy data following National Institutes of Health (NIH) policy. When requested, formal interim analyses to assess safety and efficacy will be performed. Formal interim analyses will include distributions of endpoints, biomarkers and AEs. Additional analyses may be requested by the DSMB.

15.1 *Interim Analysis for Early Stopping*

We will use the method for interim analyses described by Emerson and Fleming (Emerson & Fleming, 1989) which is implemented in the SPlus module S+SeqTrial (TIBCO_Software, 2009) to provide cut-points for an interim analysis for futility. This module does not require specifying the timing of interim analyses and controls the overall type I and type II errors. In order to make what follows clearer we provide some notation. Let p represent the true probability of a favorable outcome in islet transplanted subjects.

The efficacy hypothesis is

$$H_{01} : p \leq 0.27 \text{ versus } H_{a1} : p > 0.27.$$

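### Time-to-event outcomes start at a transplant, so a death or cardiovascular event in a subject who begins induction but never receives islets is left out of the Kaplan-Meier estimates

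*SAP*

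**What the plan says.** **Who is analysed.** Sections 5.2.1 and 5.2.3 define the modified ITT and safety populations by the start of protocol-directed therapy, not by infusion. Section 5.2.3 adds: "Subjects in this population might not receive an islet transplant". Section 14 opens with "Safety analyses will be conducted for the safety population" and goes straight on to say that its summaries cover the targeted safety endpoints as well as all observed adverse events.

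**When exposure begins.** Section 5.1.1: "eligible subjects will begin immunosuppression therapy on Day -2 (Day 0 is defined as the day of transplant").

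**Time-to-event outcomes.** Section 2.6: "All events will be defined for the period from the first transplant to 1095 days after the last islet transplant". Section 12.4 allows two time origins, "1) the time of the first transplant and (2) the time of the last transplant". The outcomes include death, cardiovascular events and a global treatment failure composite.

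**Targeted adverse events.** Section 2.7 sets the times as "At 75 ± 5 days following each transplant, at 365 ± 14 days following the first and last islet transplant(s"), with later times after the last transplant. Section 14.2 says "Results will be reported for the following time points: 75 days and one year after the first and last transplant" and continues to two and three years.

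**General adverse event rates.** Section 14.2.1 uses a different origin. It defines exposure with the words "if a subject is only followed r days after the initiation of induction immunosuppression".

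**The concern.** The analysis populations and the time-to-event clock do not match. A subject who starts induction on Day -2 and is never infused belongs to both the modified ITT and the safety population, yet has no first or last transplant and so no time zero in any survival analysis.

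The omission may not be neutral. A serious event during the two days of immunosuppression before the planned infusion can be the reason why no infusion follows. The rule could then remove the cases that a mortality or treatment-failure curve exists to show. Section 1 gives the consortium's goal as showing that the rate of favorable outcomes is high enough to justify the risks of both the procedure and the immunosuppression. A mortality curve that begins at infusion does not cover all of the second risk.

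**Working it through.** No stated figure has to be reproduced. The check compares the time origin of each output with the population it is meant to describe.

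| Output | SAP section | Time origin | Is a never-transplanted subject placed? |
|---|---|---|---|
| Primary endpoint | 10.1 | First transplant | Yes, by explicit rule: failure |
| Time-to-event outcomes | 2.6, 12.4 | First or last transplant | No |
| Targeted adverse events | 2.7, 14.2 | Cut-offs counted from a transplant; start of counting not stated | In the population, but no cut-off given |
| Adverse event rates per 100 person-days | 14.2.1, Appendix 4 | Initiation of induction (text); eligibility confirmation (Appendix 4 title) | Yes |
| Listing of individuals with events | 14.2.1, Appendix 5 | Initiation of induction (text); eligibility confirmation (Appendix 5 title) | Yes |
| Overall adverse event summaries | 14 | None needed; all available data | Yes |

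1. *The time-to-event exclusion is written, not implied.* Section 2.6 opens the event period at the first transplant, and section 12.4 offers no earlier origin. An event on Day -2 or Day -1 precedes that period. In a subject who is never infused, the period never opens.

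2. *The SAP has rules for similar cases.* Section 10.1 provides for the subject who starts immunosuppression and is never transplanted, and scores a failure. Section 12.4 itself says what to do with a subject who has already had the event by the second transplant. Neither provision covers a subject with no first transplant in the survival analyses.

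3. *Direction of the effect.* Ignoring censoring, let d of n transplanted subjects and e of m induction-only subjects have the event. The transplant-anchored rate is d/n; the rate in the whole modified ITT population is (d + e)/(n + m). The first is lower than the second exactly when e/m > d/n, that is, when events are more frequent among the induction-only subjects. That is plausible if events stop treatment, but it is not certain: leaving out event-free induction-only subjects moves the estimate the other way. The SAP gives neither m nor e, so no number can be put in.

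4. *Cost of moving the origin.* Day 0 - (Day -2) = 2 days. Against the one-year estimate this is 2/365 = 0.5% of the interval, and against three years 2/1095 = 0.2%.

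5. *A related inconsistency.* Section 14.2.1 counts from initiation of induction but sends its results to Appendices 4 and 5, whose titles count months from confirmation of transplant eligibility. That date is earlier than induction, so the titles exclude no one, but text and templates cannot both be right.

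**The case against.** **The survival analyses were meant for transplanted subjects.** Section 12.4 describes its two time points as belonging to each transplanted subject, so the restriction may be deliberate. The curves are secondary and descriptive, and outcomes such as time to HbA1c of 6.5% or less are naturally timed from infusion. This stands for the HbA1c outcomes. It does not settle the matter for death, cardiovascular events and global failure, because section 5.2.1 puts all efficacy and safety analyses on the modified ITT population and no exception is stated.

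**Harms in these subjects are reported elsewhere.** This is correct. A reader might infer from sections 2.7 and 14.2 that such harms have no place in any safety output, or that the targeted tables would use transplanted subjects only as the denominator. The SAP supports neither reading. Section 14 already makes the safety population the basis for the targeted endpoints. Section 14.2 lists reporting cut-offs and does not say that counting begins at the transplant. The rates and listing in section 14.2.1 start at induction, the Appendix 5 template includes the number and percentage of patients affected, and the overall summaries use all available events and are repeated in the final report. A death before infusion would appear there as a Grade 5 event, and in section 10.1 as a failure.

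**Such subjects should be rare.** Induction begins only once a compatible preparation is available, and section 5.3.1 expects every eligible subject with an acceptable isolation to be transplanted. That limits the likely size, but sections 5.2.3 and 10.1 both provide for the case.

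**Conclusion.** The point holds for the harm-type time-to-event outcomes. As written, a death, cardiovascular event or global treatment failure in a subject who starts induction and never receives islets is left out of the Kaplan-Meier estimates, while the same subject counts as a failure in the primary analysis.

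For the targeted adverse event tables the point is smaller. The denominator is already fixed; what is unstated is where counting starts and which cut-off applies to a subject without a transplant. The origin named in the Appendix 4 and 5 titles also disagrees with section 14.2.1.

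The size is unknown, because the SAP does not say how many subjects may start induction without a transplant. An understated event rate needs at least one such subject to have an event, and a higher event frequency in that group than among transplanted subjects. The documents neither establish nor exclude this.

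**What to change.** - **Sections 2.6 and 12.4.** For time to death, cardiovascular events and global treatment failure, set time zero at the first induction dose and include the whole modified ITT population. Keep the curves from first and last transplant as additional displays. HbA1c-based outcomes may stay anchored at transplant. Some poor-control components of the composite are themselves timed from the first transplant, so add a sentence on how they apply to a subject who has none.
- **Section 14.2.** State that targeted events count from initiation of induction, as in section 14.2.1, and that never-transplanted subjects are counted over the same number of days from induction.
- **Appendices 4 and 5.** Reconcile the time origin in the titles with the text of section 14.2.1.

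The cost is SAP wording and table programming. Section 14.2.1 already needs the date of induction for every subject, so no new data item should be required. The one drawback is a shift of about two days in the time scale for transplanted subjects, and the retained transplant-anchored curves cover that.
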